**Medical records abstraction.** During completion of the questionnaire, donors are asked to provide signed waivers for medical records requests from their primary and other care providers. Pre-donation medical records are obtained from the transplant center. Post-donation medical records are obtained from the transplant center, as available, and from the participants' medical providers over time.

**Aim 1: To assess emergency department utilization associated with caregiving among a cohort of living kidney donors who were obese at the time of donation.** We will leverage an existing multi-center R01 study of a national cohort of obese living kidney donors, to quantify the association between a donor reporting that they served as the primary caregiver for the transplant recipient and ED utilization using generalized estimating equations. We will adjust for baseline characteristics and will explore the presence of effect modification and interaction between caregiving status and donor age, race/ethnicity, and rurality.

**Study population.** The study population will consist of living donors with obesity identified by the parent R01, categorized by whether or not they served as the primary caregiver for their transplant recipient. Donors will be stratified by relationship to the recipient (parent, child, spouse/life partner, other caregiver) and sex to allow us to explore sex as a biological variable. We estimate that approximately 20% (n=5,070) were the caregiver for their recipient, of whom 40% were  $\geq 50$  years old (3%  $> 65$  years), and 17% were minorities.

**Definition of caregiver.** Donors are asked whether they served as the primary caregiver (i.e., the main individual who provided unpaid caregiving activities pre and post-donation) for their transplant recipient.

**Definition of outcome of interest.** As part of the parent R01, healthcare utilization data are obtained from the questionnaire and include whether donors have utilized the ED since donation. Donors are asked to report not only whether they used the ED as well as the frequency of use.

**Aim 2: To assess hospitalization associated with caregiving among a cohort of living kidney donors who were obese at the time of donation.** We will use the same cohort from Aim 1 to quantify the association between a donor reporting that they served as the primary caregiver for their transplant recipient and hospitalization using generalized estimating equations.

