**Study population.** The same study population identified in Aim 1 will be used.

**Definition of outcome of interest.** The parent R01 also captures data on whether the donor has been hospitalized since donation and the number of times the donor has been hospitalized.

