## STATISTICAL DESIGN AND POWER

**Aim 1. Power calculation.** Goren et al. demonstrated a significant difference in ED utilization by caregiver status (7.2% for caregivers vs. 4.0% for non-caregivers). Assuming a two-tailed test and a proportion of 4% experiencing ED use in the non-caregiver group, we will have 99% power to detect a relative risk of 1.8 for ED utilization among caregivers vs. non-caregivers. This is likely an underestimate, given that individuals with obesity have a greater use of hospital services, and incidence is likely to be higher in our cohort.

**Aim 1. Statistical analyses.** We will explore post-donation ED use by caregiver status, using generalized estimating equations (GEE) accounting for repeated measurements, to estimate whether odds of ED use differ by caregiver status. We will use Poisson regression to explore count of ED visits among those who report having used these services by caregiver status, adjusting for baseline characteristics, including demographic, socioeconomic, and health status at donation. We will explore the presence of effect modification and interaction between caregiving status and donor age, race/ethnicity, and rurality. As a sub-aim, we will explore whether utilization differs by self-reported physical, mental, and financial burden among caregiver donors.

**Aim 2. Power calculation.** Goren et al. demonstrated a significant difference in the proportion of Alzheimer's caregivers experiencing hospitalization (8.1% for caregivers vs. 5.1% for non-caregivers). Assuming a two-tailed test and a proportion of 5% experiencing hospitalization in the non-caregiver group, we will have 99% power to detect a relative risk of 1.6 for hospitalization among caregivers vs. non-caregivers. This is likely an underestimate, given that this study was performed in Japan, and hospital admissions for many preventable diseases are higher in the United States than in other countries.

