**Aim 2. Statistical analyses.** We will explore odds of post-donation hospitalization by caregiver status, first using generalized estimating equations to account for repeated measurements, then using Poisson regression to explore the counts of hospitalization among those who report having used these services. As in Aim 1, we will explore the presence of effect modification and interaction by stratification and interaction terms between caregiving status and donor age, ethnicity, and rurality, in addition to exploring the role of self-reported burden in hospitalization among the subset of caregiver donors.

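### Aim 2 states no covariate adjustment for hospitalization, and neither aim names time since donation as a model term, although both outcomes accumulate from donation

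*Combined protocol and SAP*

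**What the plan says.** Aim 2 is described twice. The PROTOCOL overview says the study will quantify "the association between a donor reporting that they served as the primary caregiver for their transplant recipient and hospitalization using generalized estimating equations" and mentions no adjustment. Under STATISTICAL DESIGN AND POWER, the Aim 2 analysis reads "We will explore odds of post-donation hospitalization by caregiver status, first using generalized estimating equations to account for repeated measurements", then a Poisson model for counts among donors who report any hospitalization. No covariates are listed. The sentence that refers back to Aim 1 concerns effect modification and interaction by age, ethnicity and rurality.

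Aim 1 is different. Its PROTOCOL overview names GEE and continues "We will adjust for baseline characteristics". Its statistical section describes the GEE as "using generalized estimating equations (GEE) accounting for repeated measurements, to estimate whether odds of ED use differ by caregiver status" and attaches the covariate set to the Poisson model: "adjusting for baseline characteristics, including demographic, socioeconomic, and health status at donation".

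Under the Aim 1 study population, a population that Aim 2 reuses, "Donors will be stratified by relationship to the recipient (parent, child, spouse/life partner, other caregiver) and sex".

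Both outcomes are cumulative. The ED data "include whether donors have utilized the ED since donation", and the hospitalization data record "whether the donor has been hospitalized since donation and the number of times the donor has been hospitalized". No section includes elapsed time as a covariate, an offset or a defined observation interval. The donor questionnaire is repeated annually, but its recall period is not stated.

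**The concern.** Caregiver status is observed, not assigned, so a crude contrast carries along whatever else differs between the groups. The imbalance was foreseeable from Table 1: caregivers had a median age of 46 against 41 in the overall cohort, and were 65.0% against 58.4% female. RESULTS shows the same pattern among the donors studied: 62.6 vs 57.9 years, and 69.6% vs 58.3% female.

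Time since donation is a separate matter. The chance of any admission, and the number of admissions, can only rise with elapsed time. Covariates fixed at donation do not capture this. A GEE that handles repeated measurements deals with correlation within a donor, not with unequal observation time. RESULTS gives one pooled median (10.4 years) and no figure by caregiver status.

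At stake is whether Aim 2's main estimate can separate an association with caregiving from age, sex and length of follow-up. As the text stands, it cannot.

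**Working it through.** **Inputs from RESULTS.** Hospitalization: 71 of 138 caregivers; 237 (40.3%) of non-caregivers. ED question: 77 of 144 caregivers; 305 (49.4%) of non-caregivers. Pooled median follow-up: 10.4 years.

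**Denominators.** Those for non-caregivers are not printed.
- Hospitalization: 237/587 = 40.37%, 237/588 = 40.31%, 237/589 = 40.24%. Only 588 rounds to 40.3%.
- ED: 305/617 = 49.43% and 305/618 = 49.35%. Both round to 49.4%.

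**Reported percentages.** 71/138 = 51.4% (printed as 51.5%); 77/144 = 53.5%.

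**Crude hospitalization odds ratio.**
- OR = (71 × 351)/(67 × 237) = 1.569.
- SE of log OR = √(1/71 + 1/67 + 1/237 + 1/351) = 0.190.
- 95% CI = 1.569 × exp(±1.96 × 0.190) = 1.08 to 2.28; uncorrected chi-square p = 0.017.

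**Crude ED odds ratio.** (77 × 312)/(67 × 305) = 1.18 (0.82 to 1.69), p = 0.38. With 618 it is 1.18 (0.82 to 1.70), p = 0.37.

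**Illustration 1: age.** The age effect is an assumption, and the interval width is held fixed. The gap is 62.6 − 57.9 = 4.7 years, so an age odds ratio of k per decade divides the crude estimate by k^0.47.

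| Assumed k per decade | Divisor | Shifted OR (95% CI) |
|---|---|---|
| 1.10 | 1.046 | 1.50 (1.03 to 2.18) |
| 1.18 | 1.081 | 1.45 (1.00 to 2.11) |
| 1.30 | 1.131 | 1.39 (0.96 to 2.01) |
| 2.00 | 1.385 | 1.13 (0.78 to 1.64) |

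The lower limit reaches 1 at 1.0816^(1/0.47) = 1.18 per decade. The point estimate reaches 1 only at 1.569^(1/0.47) = 2.61 per decade.

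**Illustration 2: follow-up.** This assumes a constant first-hospitalization rate and 10.4 years in non-caregivers. Rate = −ln(1 − 0.4031)/10.4 = 0.0496 per year.
- Caregivers 1 year longer: expected proportion 0.432, odds shift 1.126, OR 1.39 (0.96 to 2.02).
- Caregivers 1 year shorter: expected proportion 0.373, odds shift 0.880, OR 1.78 (1.23 to 2.59).
- Removing the association would take 14.56 years, about 4.2 years longer.

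The two illustrations should not be multiplied together. RESULTS does not say whether its ages are at donation or at survey. Against Table 1's medians of 46 and 41, age at survey looks likely, and the 4.7-year gap would then already contain any follow-up difference.

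**Sex.** With 69.6% vs 58.3% female, an assumed sex risk ratio of 1.2 gives a bias factor of (1 + 0.696 × 0.2)/(1 + 0.583 × 0.2) = 1.02; an assumed 2.0 gives 1.696/1.583 = 1.07. Sex alone is minor.

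**Form of the time term.** The count models include only users, so counts start at 1. For Poisson counts the mean among users is μ/(1 − e^−μ).
- At 10.4 years, μ = 0.516 and the mean is 1.280.
- At 11.4 years, μ = 0.566 and the mean is 1.309, a rise of 2.3%.
- A log-time offset would impose 11.4/10.4 − 1 = 9.6% and over-correct.

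**The case against.** The strongest reply is that Aim 2 is written as shorthand for Aim 1: same cohort, same study population, an explicit reference back. A shared covariate set may well have been intended, and a model with an age interaction would contain age. Stratification by sex and relationship is also planned. This stands as a statement of likely intention. It does not supply the missing text: the reference back governs effect modification only, and exploratory strata and interactions do not define an adjusted main estimate. None of them involves elapsed time.

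Second, the harm from follow-up is hypothetical. That is correct. No difference by caregiver status is reported, and every age and follow-up effect above is assumed.

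A reader might also infer that Aim 1's ED model is unadjusted, because its sentence in the statistical section names no covariates. The documents do not support that. The PROTOCOL overview names GEE as the Aim 1 model and then commits to baseline adjustment. Only the time term is missing there.

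**Conclusion.** The point holds as an omission from the plan. Aim 2 states no adjustment, and neither aim names time since donation as a model term. Run as written, Aim 2's main contrast would be crude between groups that differ in age and sex.

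The size of the problem is uncertain. The crude hospitalization odds ratio of 1.57 (1.08 to 2.28) rests on an inferred denominator of 588. Its lower limit is sensitive to a modest assumed age effect or one assumed extra year of follow-up. Its point estimate is more robust, needing about 2.6 per decade or about 4.2 extra years to vanish.

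A reader might conclude that the observed hospitalization difference is an artefact of confounding. The documents do not support that: they give no size or direction for net confounding, RESULTS makes no inferential claim about hospitalization, and shorter follow-up in caregivers would move the estimate upward. Nor do they say whether an adjusted analysis has already been run. The change should be made, because it is cheap and affects how the main Aim 2 estimate can be read.

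**What to change.** 1. State that Aim 2's GEE and count models adjust for the Aim 1 baseline set: demographic factors, including age at donation and sex, socioeconomic factors, and health status at donation. Using age at donation keeps age distinct from elapsed time.
2. In both aims, add time since donation as a covariate in the GEE and count models. Do not use a log-time offset in count models restricted to users.
3. Report adjusted estimates with 95% CIs beside the crude percentages for both outcomes, and time since donation by caregiver status.
4. Report how many donors each adjusted model loses to missing covariates.

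Aim 1's GEE needs no new baseline adjustment.

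The cost is a sentence or two of wording and slightly more analysis. The downside is possible loss of donors with missing covariates; the documents do not say how complete health status at donation is.

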## RESULTS

Among 784 donors (median 10.4yrs post-donation), 148 (18.9%) identified as caregivers. Caregiver donors were older (62.6 vs. 57.9yrs,  $p < 0.001$ ), more often female (69.6% vs. 58.3%,  $p=0.01$ ), the recipient's spouse (50.0% vs. 7.9%) or parent (16.2% vs. 4.6%,  $p < 0.001$ ), and retired (38.4% vs. 24.9%,  $p=0.004$ ), with no racial differences. Among those identifying as the caregiver and responding to the question about hospitalization ( $n=138$ ), 71 (51.5%) reported having been admitted to the hospital since donation, compared to 237 (40.3%) among non-caregivers. Among those identifying as the caregiver and responding to the question about emergency room utilization since donation ( $n=144$ ), 77 (53.5%) reported having been admitted to the hospital since donation, compared to 305 (49.4%) among non-caregivers.

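### The only Aim 1 (emergency department) result is labelled as hospital admission, and its non-caregiver count cannot be admissions if the preceding sentence is right

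*Combined protocol and SAP*

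**What the plan says.** The Protocol section keeps two outcomes apart. Under Aim 1, "healthcare utilization data are obtained from the questionnaire and include whether donors have utilized the ED since donation"; under Aim 2, the outcome is hospitalization since donation, captured as its own item. The Aim 1 statistical analysis is planned "to estimate whether odds of ED use differ by caregiver status".

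The Results section opens with the cohort: "Among 784 donors (median 10.4yrs post-donation), 148 (18.9%) identified as caregivers". Two utilization sentences follow.

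- The first concerns the 138 caregivers who answered the hospitalization question: "71 (51.5%) reported having been admitted to the hospital since donation, compared to 237 (40.3%) among non-caregivers".
- The second concerns the 144 caregivers "responding to the question about emergency room utilization since donation". Its result reads: "77 (53.5%) reported having been admitted to the hospital since donation, compared to 305 (49.4%) among non-caregivers".

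Non-caregiver denominators are not printed in either sentence.

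**The concern.** The second sentence names one question when it sets its denominator and a different outcome when it gives its result. Both parts cannot be right. This sentence is also the only place in the document where an ED result could be, so the label decides which aim the figures answer.

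A reader who quotes the sentence as printed would report 53.5% versus 49.4% as hospitalization. That reader would also hold a second, different hospitalization result (51.5% versus 40.3%) and would conclude that Aim 1 has no result. The two contrasts differ enough for the label to matter: crudely, one is about 11 percentage points and the other about 4.

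**Working it through.** **Inputs, all from the Results section.** 784 donors; 148 caregivers. Hospitalization sentence: 71 of 138 caregivers (51.5%) and 237 non-caregivers (40.3%). Second sentence: 77 of 144 caregivers (53.5%) and 305 non-caregivers (49.4%).

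**Step 1. Reproduce the printed percentages.**
- 148/784 = 18.88%, printed as 18.9%: agrees.
- 77/144 = 53.47%, printed as 53.5%: agrees.
- 71/138 = 51.449%, which rounds to 51.4%; 51.5% is printed. This is a small, separate slip.

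**Step 2. Recover the non-caregiver denominators.** Non-caregivers: 784 − 148 = 636.
- For 237 at 40.3%: 237/587 = 40.4%, 237/588 = 40.3%, 237/589 = 40.2%. Only 588 fits.
- For 305 at 49.4%: 305/617 = 49.43% and 305/618 = 49.35%. Both fit.

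**Step 3. Bound the number of admitted non-caregivers.** Non-responders to the hospitalization question: 636 − 588 = 48. The largest possible number of admitted non-caregivers counts every one of them as admitted:

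maximum = reported admissions + non-responders = 237 + 48 = 285.

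The second sentence prints 305, which exceeds the maximum by 305 − 285 = 20.

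**Step 4. Test the bound against rounding.** For a hospitalization denominator n, the maximum is 237 + (636 − n).

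| n | Maximum admitted |
|---|---|
| 586 | 287 |
| 588 | 285 |
| 590 | 283 |

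To reach 305, at least 305 − 237 = 68 non-caregivers must not have answered, so n could be at most 636 − 68 = 568. The printed percentage would then be at least 237/568 = 41.7%, not 40.3%. A rounding slip like the one in Step 1 does not close that gap.

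**Step 5. Apply the same bound to caregivers.** Non-responders: 148 − 138 = 10. Maximum: 71 + 10 = 81, which is not below 77. The caregiver counts alone therefore prove no conflict; the contradiction rests on the non-caregiver count.

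**Step 6. See what the label changes.** Crude risk differences d = p₁ − p₂ with Wald limits d ± 1.96·√[p₁(1−p₁)/n₁ + p₂(1−p₂)/n₂]:

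| Contrast | Difference (points) | 95% CI |
|---|---|---|
| 71/138 vs 237/588 (hospitalization) | 11.1 | 1.9 to 20.4 |
| 77/144 vs 305/617 (second sentence) | 4.0 | −5.0 to 13.1 |
| 77/144 vs 305/618 (second sentence) | 4.1 | −4.9 to 13.2 |

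These are unadjusted, use back-calculated denominators and are not the planned generalized estimating equation (GEE) estimates. They show only that the two sets of figures would be read differently.

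**The case against.** The strongest reply is that this is an obvious clerical carry-over. The sentence itself names the emergency-room question, the sentence before it handles hospitalization, and a careful reader will infer what was meant. Correcting the phrase changes no count or percentage, and no design or model choice depends on it. On that view the correction is warranted but minor.

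A second line is about certainty. The bound shows that the two sentences cannot both be right as labelled; it does not show that 77 and 305 are ED users. The denominators 588 and 617 or 618 are inferred from rounded percentages in a paragraph that contains at least one rounding slip. If a wrong variable was tabulated, changing a phrase would not be enough.

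The points about certainty stand, and the conclusion and fix are conditioned on them. The argument for treating the error as minor does not: readers can guess the intent but cannot verify it, and the sentence is the sole statement of one aim's outcome. Doubt about the denominators does not rescue the literal reading either, since Step 4 shows how far n would have to move. If some of the 784 left the caregiver question blank, there would be fewer than 636 non-caregivers and the bound would only tighten.

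**Conclusion.** The sentence is wrong as written and must be corrected. Its denominator and its outcome refer to different questions, which is visible without any calculation. Read literally, it also needs 305 admitted non-caregivers where the preceding sentence allows at most 285.

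The bound assumes that donors answered the two questions consistently, that non-caregivers number at most 636, and that the preceding sentence is correct to within ordinary rounding. That the figures are really ED use is the most plausible explanation, but it is an inference from the denominator wording and not something the document establishes.

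**What to change.** 1. Check 77 and 305 against the source data.
2. If they are ED-use counts, change the outcome phrase to say that these donors reported having used the emergency department since donation.
3. If they are not, tabulate the ED result from the correct variable and replace the sentence.
4. In the same edit, print the non-caregiver denominators from the source data. The back-calculated values (588 for hospitalization; 617 or 618 for the ED question) serve only as a check.
5. Recheck 71/138 and its printed percentage.

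If step 1 confirms ED use, the cost is one source check and a few words, with no re-analysis. Only the outcome in step 3 would require a new tabulation.
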